10.11. PREMATURE TERMINATION OR SUSPENSION OF A STUDY	
10.12. Adherence to protocol	
11. REFERENCES	
APPENDIX 1: AMENDMENT 01	46

LIST OF TABLES

Table 1. Study Design and Schedule of Assessments	. 43
Table 2. Blood Sampling Schedule	. 44
Table 3. Pharmacokinetic Parameters	. 45

STUDY SYNOPSIS

Title of Study :	Single Dose Pharmacokinetic Study to Assess the Systemic Exposure of Chlorhexidine from ReadyPrep [®] CHG (2% Chlorhexidine Gluconate Cloth)	
Phase:	Phase I study	
Investigational Pro	duct : ReadyPrep [®] CHG (2% Chlorhexidine Gluconate Cloth) Manufacturer: Medline Industries, Inc., USA	
Treatments:	Treatment-1: Abdominal application of ReadyPrep [®] CHG	
	Treatment-2: Groin application of ReadyPrep [®] CHG	
	Treatment-3: Control treatment with no application	
Objective :	The primary objective of this study is to demonstrate that no or negligible systemic exposure occurs after a single topical application of ReadyPrep [®] CHG.	
	The secondary objective of this study is to determine the safety and tolerability of a single topical application of ReadyPrep [®] CHG in healthy volunteers after a single topical application.	
Study Design:	Single center, randomized, single dose, laboratory-blinded, 3-period, 3- sequence, crossover design.	
Subjects :	Twelve (12) subjects will be included in the study	
Main Inclusion Cri	teria: Male and female volunteers, non- or ex-smokers, ≥ 18 and ≤ 60 years of age (inclusive) with a body mass index (BMI) greater than or equal to 19.00 and below or equal to 32.00 kg/m ² and a body weight ≥ 55 kg will be selected according to the inclusion and exclusion criteria. They will be healthy according to medical history, complete physical examination (including vital signs and skin examination) and laboratory tests (general biochemistry, hematology, urinalysis) including negative Human Immunodeficiency Virus (HIV), Hepatitis B and Hepatitis C tests as well as negative drug screening of alcohol, and drugs of abuse. For female subjects, a pregnancy test must be negative.	
Administration:	In Treatment-1 and -2, a single topical application of ReadyPrep [®] CHG consisting of a 3-minute vigorous rub followed by a 1 minute dry time will be done at the application site. In one study period, the application site	

will be the abdomen (surface area of approximately 5 x 5 inches) and in the other study period, the application site will be the groin (surface area of approximately 5×2 inches).

Treatment-3 will consist of a control treatment where the same procedures as Treatment-1 and -2 will be performed, but without the topical application of ReadyPrep[®] CHG.

Subjects will remain seated for at least the first 4 hours following each treatment.

- Blood Sampling: In each study period, 12 blood samples will be collected. Baseline levels will be assessed before each treatment. For baseline assessment, 3 blood samples will be collected prior to each treatment while the others will be collected up to 24 hours after each treatment.
- **Housing**: From at least 10 hours prior to each treatment until 24 hours following each treatment.
- **Wash-out**: The treatment will be separated by at least 7 calendar days.
- **Tests during study**: Drug and alcohol screening will be performed before each period of the study.

For female subjects, a pregnancy test will be performed before each period of the study.

General biochemistry tests will be performed before each period of the study.

Vital signs will be measured prior to and approximately 12 and 24 hours following each treatment.

Visual skin evaluation at the application site will be performed prior to and approximately 4, 8 and 24 hours after treatment.

Poststudy Tests: Hematology, general biochemistry tests (including a pregnancy test for female subjects) and urinalysis will be repeated at the end of the study.

A complete physical examination (including vital signs) will be performed.

Safety data: Safety will be evaluated through the assessment of adverse events (AE), laboratory tests, vital signs, visual skin evaluation and physical examination.

Bioanalysis: Chlorhexidine plasma concentrations will be measured by a validated bioanalytical method.

- **Pharmacokinetics:** In the event that chlorhexidine levels are measurable, the pharmacokinetic parameters will be estimated with and without baseline adjustment. Main absorption and disposition parameters will be assessed using a non-compartmental approach with a log-linear terminal phase assumption. Trapezoidal rule will be used to estimate the area under the curve. The pharmacokinetic parameters of interest will be C_{max} , AUC_{0-T} and AUC_{0- ∞}. Other parameters including T_{max} , AUC_{0-T/ ∞}, λ_{Z_c} , T_{half_c} Cl/F and V_d /F will be calculated and provided for information purposes only.
- **Statistics**: No statistical analysis will be performed.

LIST OF ABBREVIATIONS AND DEFINITION OF TERMS

1. INTRODUCTION

Chlorhexidine [CHD; 1,1'-hexamethylenebis[5-(4-chlorophenyl) biguanide]] has a wide spectrum of bactericidal and antiviral activity and is a common ingredient in various formulations ranging from skin disinfectants in healthcare products to antiplaque agents in dentistry. The presence of two symmetrically positioned basic chlorophenyl guanide groups attached to a lipophilic hexamethylene chain aid in rapid absorption through the outer bacterial cell wall, causing irreversible bacterial membrane injury, cytoplasmic leakage, and enzyme inhibition. Chlorhexidine exists as various forms of salts: diacetate, dihydrochloride, or digluconate, mainly differing by their solubilizing abilities in aqueous or oily media. Chlorhexidine digluconate (or gluconate), as most soluble in water or alcohol, is the most used form in topical dermatology or cosmetic preparations.^{1,2}

As chlorhexidine is not significantly absorbed through intact skin³ no systemic adverse events are expected. However, skin reaction could occur.

ReadyPrep[®] CHG is composed of 2% chlorhexidine gluconate (CHG) solution on a single fiber, polyester cloth. Each cloth contains 500 mg CHG. The sponsor is developing ReadyPrep[®] CHG (2% Chlorhexidine Gluconate Cloth) for patient preoperative skin preparation.

In order to better understand and control for the presence of chlorhexidine in the environment, baseline levels will be assessed in each study period and a control treatment arm will be included.

2. STUDY OBJECTIVES

The primary objective of this study is to demonstrate that no or negligible systemic exposure occurs after a single topical application of ReadyPrep[®] CHG.

The secondary objective of this study is to determine the safety and tolerability of a single topical application of ReadyPrep[®] CHG in healthy volunteers after a single topical application.

3. STUDY TREATMENTS

3.1. INVESTIGATIONAL PRODUCT

ReadyPrep[®] CHG (2% Chlorhexidine Gluconate Cloth) Manufacturer: Medline Industries Inc., USA

DOSAGE FORM: Cloth for topical application.

DOSAGE: Single topical application of ReadyPrep[®] CHG (2% Chlorhexidine Gluconate Cloth) on either the abdomen or the groin.

The investigational product will be provided by the sponsor. The lot number and the measured content of the dosage form (when available) will be included in the final report.

3.2. PACKAGING AND LABELING

The sponsor will be responsible for ensuring the investigational product is manufactured in accordance with Good Manufacturing Practice (GMP); the labeling should also comply with applicable regulatory requirement(s).

The investigational products will be dispensed according by Algorithme Pharma, unless the sponsor supplies Algorithme Pharma with pre-labeled individual dosing samples.

3.3. RANDOMIZATION AND UNBLINDING PROCEDURES

3.3.1. Treatment assignment

Algorithme Pharma will generate the randomization code with a computer program according to the study design, the number of subjects and the sequence

of treatment. The random allocation of each sequence of treatment to each subject will be done in such a way that the study is balanced. Once generated, the randomization code will be final and will not be modifiable.

3.3.2. Un-blinding procedure

The randomization code will not be available to the personnel of the bioanalytical facility until the bioanalytical tables have been finalized and audited by the Quality Assurance (QA) department.

3.4. DRUG ACCOUNTABILITY

Algorithme Pharma will maintain an inventory record of the investigational products received, stored in a secure restricted area, and dispensed as per State law. Investigational products will be provided to study subjects only.

At the conclusion of the study, all unused investigational products and all medication containers will be returned to the sponsor unless the sponsor has approved other arrangements. A final report of investigational product accountability will be prepared and maintained.

4. STUDY DESIGN AND DURATION

In two study periods, the ReadyPrep[®] CHG formulation will be administered as a single topical application to either the abdomen or the groin. Another study period will consist of a control treatment without topical application of ReadyPrep[®] CHG.

Treatment-1: Abdominal application of ReadyPrep[®] CHG

Treatment-2: Groin application of ReadyPrep[®] CHG

Treatment-3: Control treatment with no application

Twelve (12) healthy male or female subjects will be included in the studyaccording to the following randomized, 3-sequence, 3-period, crossover design:

	Period 1	Period 2	Period 3
Sequence 1 (n= 4)	Treatment-1	Treatment-2	Treatment-3
Sequence 2 $(n=4)$	Treatment-2	Treatment-3	Treatment-1
Sequence 3 (n= 4)	Treatment-3	Treatment-1	Treatment-2

The drug applications will be separated by at least 7 calendar days. The duration of the clinical part of this study is expected to be approximately 17 days. The actual overall study duration may vary.

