6.1.2.1. Drug administration procedure

ReadyPrep[®] CHG Application (Treatment-1 and Treatment-2):

In two Treatment-1 and -2, a single topical application of ReadyPrep[®] CHG will be done on either the abdomen (surface area of approximately 5 x 5 inches) or the groin (surface area of approximately 5 x 2 inches) according to the randomization scheme.

The drug will be applied to a clean, dry, non-irritated, normal skin area. Possible hairs will be removed by means of scissors (no shaving) on the morning of dosing.

Approximately 30 minutes prior to any application, the site should be gently washed with room temperature water and dried without rubbing or heavy pressure with a gauze or similar cotton soft material. The application site must be allowed to dry for at least 15 minutes before drug application. After drying, the application site will be marked for dose location.

The topical application of ReadyPrep[®] CHG will consist of a 3-minute vigorous rub followed by a 1 minute dry time at the application site. The

1-minute dry time will be air drying without dabbing or rubbing. The time of dosing will be defined as the start time of the drug application on the skin.

Control Treatment (Treatment-3):

In Treatment-3, the same procedures as Treatment-1 and -2 will be performed, but without the topical application of ReadyPrep® CHG or placebo (no placebo ReadyPrep[®] cloth will be provided or used). Therefore, approximately 30 minutes prior, the site should be gently washed with room temperature water and dried without rubbing or heavy pressure with a gauze or similar cotton soft material. The application site must be allowed to dry for at least 15 minutes and after drying, the skin site will be marked. Subjects should be placed in the same position, for the same length of time, in the same area as they would be dosed.

The physician will remain at the clinical site for at least the first 4 hours following each treatment and will remain available at all times during the entire period of the study.

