6.3.3. Visual skin evaluation

Visual skin evaluation of the application site will be performed by the physician in charge or designee as follows:

Application site verification (for redness, markings, scars, etc.) will be documented prior to and approximately 4, 8 and 24 hours after each treatment.

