9.2. PHARMACOKINETIC ANALYSIS

No or negligible plasma levels of chlorhexidine are expected following a single topical application of ReadyPrep[®] CHG. Chlorhexidine plasma concentrations produced by each treatment will be determined in order to establish the pharmacokinetic profile of the drug product. Below limit of quantitation concentrations (coded BLQ) will be treated as zero for all statistical analyses. In the event that chlorhexidine levels are measurable, the pharmacokinetic parameters that will be derived from the plasma concentrations (see Section 6.2.1) will be taken into consideration for evaluation of PK parameters.

In the case where concentrations of chlorhexidine cannot be determined due to bioanalytical or clinical reasons, these values will be set to missing for the pharmacokinetic analysis.

In the case where less than 3 consecutive measurable concentrations of chlorhexidine are observed, the AUC parameters will not be estimated for that specific study period.

In order to better understand and control for the presence of chlorhexidine in the environment, baseline levels will be assessed in each study period. The pharmacokinetic parameters for chlorhexidine will be presented both adjusted for baseline and unadjusted. The baseline adjustment will consist of the following:

- Baseline concentrations will be measured approximately 10.00, 2.00 and 0.50 hours prior to each treatment. The mean of these 3 pre-dose concentrations will be used for baseline adjustment.
- Concentrations post-dose will be adjusted for each subject during each period by subtracting the mean baseline value corresponding to that subject. Baseline adjustment will therefore be subject- and period- specific.

If subtraction leads to values of adjusted profile that would be below the LOQ, these values will be reported without any change and they will not be reported as BLQ. However, if a negative plasma concentration value results after baseline adjustment, this value will be set to 0 prior to calculating the baseline-adjusted AUC.

For baseline adjusted calculations, concentrations at time T= -0.50 h will be set to zero given that no concentration provided by the given treatment is expected to be present at this time point. Unadjusted baseline PK estimation will use the observed concentration value at time T=-0.50 h.

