The main pharmacokinetic parameters of interest for this study will be C_{max} , AUC_{0-T} and $AUC_{0-\infty}$. Other parameters such as T_{max} , $AUC_{0-T/\infty}$, λ_Z and T_{half} will be provided for information purposes only.

The main absorption and disposition parameters will be estimated using a non-compartmental approach with a log-linear terminal phase assumption. The trapezoidal rule will be used to estimate the area under the curve (linear trapezoidal linear interpolation) and the terminal phase will be estimated by maximizing the coefficient of determination estimated from the log-linear regression model. However, $AUC_{0-\infty}$, $AUC_{0-T/\infty}$, λ_Z and T_{half} parameters will be estimated for individual concentration-time profiles only when the terminal log-linear phase can be reliably characterized using the following criteria:

- Phoenix[®] WinNonlin[®] Best fit range selection
- R^2 of at least 80%
- The corresponding terminal half-life value must be lower than or equal to 2 times the time interval over which λ_Z was estimated (i.e. $T_{half} \leq$ twice the time interval difference between T_{LQC} and T_{LIN}).

Descriptive statistics will be calculated for plasma concentrations at each individual time point and for all pharmacokinetic parameters. The individual plasma concentration/time profiles will be presented using the actual sampling times whereas the mean plasma concentration/time profiles will be presented using the theoretical sampling times.

Pharmacokinetic analyses will be generated using validated pharmacokinetic software (i.e. Phoenix[®] WinNonlin[®] version 6.3 or higher, Phoenix[®] ConnectTM version 1.3.1 or higher).

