9.3. STATISTICAL ANALYSIS

No statistical analysis will be performed.

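### Does using only three of the six possible treatment orders leave the crossover badly balanced for carryover?

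*Protocol*

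**What the plan says.** Section 4 sets out "the following randomized, 3-sequence, 3-period, crossover design". Treatment-1 is abdomen, Treatment-2 groin and Treatment-3 a control without application. The three sequences are 1-2-3, 2-3-1 and 3-1-2, with n = 4 each, and applications are at least 7 calendar days apart. Section 3.3.1 asks that the allocation of sequences be balanced and adds: "Once generated, the randomization code will be final and will not be modifiable".

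Section 9.2 expects no or negligible plasma levels. If levels are measurable, PK parameters are reported in two ways. For the adjusted version, "Concentrations post-dose will be adjusted for each subject during each period by subtracting the mean baseline value corresponding to that subject"; that baseline is the mean of samples at -10, -2 and -0.5 h in the same period. For the other version, "Unadjusted baseline PK estimation will use the observed concentration value at time T=-0.50 h". The planned output is descriptive: "Descriptive statistics will be calculated for plasma concentrations at each individual time point and for all pharmacokinetic parameters". Section 9.3 reads in full: "No statistical analysis will be performed".

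The objectives (Section 2, and again in Section 9.4 for the primary one) are negligible systemic exposure after a single application, and safety and tolerability. Neither asks for a comparison of abdomen with groin.

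**The concern.** Three treatments can be given in six orders, and the protocol uses three without saying why. In the cyclic square each treatment has one fixed predecessor. If an application left a residue into the next period, it would fall on groin and control but never directly on abdomen. The control period, added as the reference for environmental chlorhexidine, would when not first always directly follow groin.

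Abdomen is the first exposure in twice as many subjects as groin, which might seem to matter for the skin evaluation. Because no analysis is planned that could model carryover, balance by design looks like the only safeguard. Six orders with two subjects each would provide it at the same N. At stake would be the descriptive comparisons of sites and of active with control, mainly for the unadjusted PK parameters.

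**Working it through.** **Inputs.** The three sequences with n = 4 each (Section 4), and treated areas of 5 x 5 = 25 and 5 x 2 = 10 square inches (Section 6.1.2.1). The protocol gives no carryover size. Let c1 and c2 (both >= 0) be the carryover from abdomen and groin into the next period's unadjusted PK.

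**Layout.** 3 x 4 = 12, as printed. Each treatment appears 4 times in each period, so treatment is orthogonal to period and to subject. Contrasts are then simple differences of treatment means.

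**Counts.**

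| | Three orders x 4 | Six orders x 2 |
|---|---|---|
| Abdomen then groin; groin then control; control then abdomen | 8 each | 4 each |
| Reverse pairs | 0 each | 4 each |
| First exposure, abdomen : groin | 8 : 4 | 6 : 6 |
| Control periods directly after an application | 8 of 12 | 8 of 12 |

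**Precision without carryover terms.** Variance of a treatment difference = 2 sigma^2/12 = 0.167 sigma^2 in both designs. If one 1-2-3 subject is lost, least squares with subject and period effects gives 0.183 sigma^2 in both.

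**Carryover into each treatment mean** (share of the 12 periods with that predecessor, times its carryover):

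| Mean | Three orders | Six orders |
|---|---|---|
| Abdomen | 0 | (4/12)c2 |
| Groin | (8/12)c1 | (4/12)c1 |
| Control | (8/12)c2 | (4/12)(c1 + c2) |

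**Bias in the contrasts** (difference of the rows above):

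| Contrast | Three orders | Six orders |
|---|---|---|
| Abdomen - control | -0.67c2 | -0.33c1 |
| Groin - control | 0.67(c1 - c2) | -0.33c2 |
| Abdomen - groin | -0.67c1 | 0.33(c2 - c1) |

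The largest absolute bias is 0.67 max(c1, c2) now and 0.33 max(c1, c2) with six orders, so it is halved for any c1 and c2. What matters is which contrast gains and which loses.

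**Equal carryover, c1 = c2 = c.** The three contrasts go from -0.67c, 0, -0.67c to -0.33c, -0.33c, 0. Groin-control gets worse. The average active-minus-control bias is (-0.67 + 0)/2 = -0.33c now and (-0.33 - 0.33)/2 = -0.33c with six orders, so it does not change.

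**Carryover proportional to area** (assumption: c1 = 2.5c2, so c2 = 0.4c1), in units of c1:

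| | Three orders | Six orders |
|---|---|---|
| Control mean | 0.67 x 0.4 = 0.267 | 0.33 x 1.4 = 0.467 |
| Abdomen mean | 0 | 0.33 x 0.4 = 0.133 |
| Groin mean | 0.667 | 0.333 |
| Abdomen - control | -0.267 | -0.333 |
| Groin - control | +0.400 | -0.133 |
| Abdomen - groin | -0.667 | -0.200 |
| Average active - control | (-0.267 + 0.400)/2 = +0.067 | (-0.333 - 0.133)/2 = -0.233 |

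Six orders help the groin mean and the abdomen-groin contrast. They put more carryover into the control, put some into abdomen, where there is now no first-order carryover, and make both active-control differences negative. Negative bias understates exposure, which is the unfavourable direction in a study meant to show that exposure is negligible.

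**Skin.** Each subject receives one application at each site. Each site's application is therefore its first in all 12 subjects under either design. The 8:4 split counts only if treating one site changes the reaction at the other, and the protocol names no such effect.

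**The case for a change.** The strongest case for changing the design is that the change is cheap and the imbalance is avoidable. Six orders keep N, periods, visits, samples and precision, equalise all predecessor pairs, and halve the worst-case bias for any c1 and c2. If carryover were modelled, the variance of a treatment contrast would be 0.833 sigma^2 now against 0.208 sigma^2 with six orders. The randomisation code is final once generated, so the time to ask would be before that.

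The counts and coefficients stand; the conclusion does not follow from them. The variance advantage needs a carryover model that Section 9.3 rules out. Halving the largest bias is a minimax property: in the area-proportional case it benefits abdomen versus groin, while abdomen-control and the active-control average get worse. The cost is also more than a new list, because changing the sequences means a protocol amendment with IRB submission (Section 10.12), and the document does not show whether the code already exists. Giving no reason for the choice of orders is at most a missing detail.

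**Conclusion.** The concern does not hold. The cyclic square is a standard period-balanced design, is internally consistent and meets the balance that Section 3.3.1 requires. Six orders would be equally valid and equally precise (0.167 sigma^2), with no consistent advantage on the active-control differences: the average bias stays at -0.33c under equal carryover and moves from +0.07c1 to -0.23c1 under area-proportional carryover.

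All these biases are multiples of a carryover that the protocol gives every reason to expect near zero. Applications are at least 7 days apart and negligible levels are expected even after dosing. Three pre-dose samples per period would show any measurable residue, and the adjusted parameters subtract it by subject and period. Only unadjusted descriptive summaries remain open to it. There, carryover can only raise the levels seen in an active period, which works against a claim of negligible exposure. That claim rests on the levels after each application, not on a contrast between treatments.

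This rests on non-negative first-order carryover. The area-proportional ratio is an assumption used to show direction; the protocol gives no carryover figure.
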